2.2 Secondary (for the intervention study group)

The secondary objectives are to compare in the evolocumab and placebo groups:

a. Serial serum markers of inflammation, platelet and endothelial cell function, lipids, and myocardial injury, and left ventricular function which will be collected at pre-randomization, during hospitalization, at hospital discharge and at 25-30 days, 6 months and 12 months follow up. In those who are discharged before day 3, and those who are unwilling or unable to return to the hospital, additional samples may be obtained in the out of hospital setting.

The time points of comparison are pre-randomization, during hospitalization, at hospital discharge, and any obtained in the outpatient setting including the 30 days, 6 months, and 12 months samples.

- i. PCSK-9
- ii. Soluble LOX-1
- iii. IL-6, IL-10, IL-12
- iv. hsCRP
- v. platelet function
- vi. LDL-Cholesterol
- vii. HDL-Cholesterol
- viii. Triglycerides
- ix. Total Cholesterol
- x. Apolipoprotein B
- xi. Lipoprotein (a)
- xii. Troponin
- xiii. Pro-BNP
- xiv. HbA1c
- xv. Insulin
- b. The change between hospitalization and thirty day of:
 - i. PET-FDG assessed myocardial inflammation and vascular inflammation in the most diseased segment of aorta or carotid artery. For this outcome, separate analyses will also be performed in those who did and did not undergo the initial PET scan within 48 hours of study drug administration.
 - ii. Echo assessed regional wall motion in the infarct territory
 - iii. Echo assessed global LV function
 - iv. Echo assessed LV systolic and diastolic volumes

The times of collection will be at early hospitalization and 30 days. The time point of comparison will be at 30 days

c. At thirty days:

- i. Comparison of PET-FDG assessment of myocardial inflammation and vascular inflammation in the evolocumab versus placebo group as described in 2.2. b i
- ii. Echo assessed as described in 2.2. b ii-iv
- iii. Angina class
- iv. New York Heart Association functional class
- v. Serum markers as described in 2.2. a

d. At six months

- i. Angina class
- ii. New York Heart Association functional class
- iii. Echo assessment as described in 2.2. b ii-iv

In a subset of participants: The change between early infarction period and six months assessments of Cardiac MRI-assessed adverse remodeling, e.g. LV function and volumes, infarct size and scar quantification

e. At 12 months

Serum markers as described in 2.2 a

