This is a phase 2, double-blind, randomized, placebo controlled clinical trial of 420 mg evolocumab administered subcutaneously using an autoinjector/pen in NSTEMI and STEMI patients during early hospitalization at the Johns Hopkins Hospital and the Johns Hopkins Bayview Medical Center. The placebo and evolocumab will be given exactly the same way with the same Amgen provided device. All participants will receive standard care for NSTEMI and STEMI, including, as appropriate, high dose statin, aspirin, beta blocker, an angiotensin converting enzyme inhibitor or angiotensin receptor blocker, as well as angiography and reperfusion. High dose statin therapy consists of atorvastatin 40mg or 80mg or rosuvastatin 20mg or 40mg per the most recent ACC/AHA guidelines. [41] After signing informed consent, subjects will be randomized to receive one dose of evolocumab or matching placebo subcutaneously. Research blood samples for lipid profile, endothelial function, and inflammatory markers, and PET imaging assessment of myocardial and vascular inflammation as well as any clinically indicated echocardiographic studies for left ventricular function will also be obtained. Additionally, in a subset of patients we will obtain cardiac MRI studies. An independent Data and Safety Monitoring Committee will review all potential side effects and clinical outcomes during the six months of follow-up.

FDG/PET scans are not performed at Hopkins Bayview. If participants enrolled at that site are transferred to Hopkins Hospital for clinical care, and the scan can be performed during that hospitalization, it will be done so. For other patients, i.e. those discharged home from Bayview, or Hopkins patients who could not undergo the scan during their admission because of scheduling issues, the first scan will be performed on an outpatient basis. In those instances a car service will be arranged to transfer the participants to and from JHH and they will have three outpatient visits, for the initial and the follow-up 30 day scans, and for the six-month visit.

After hospital discharge, we will send a letter to the participant's physician(s) to inform them that the participant was enrolled in the study and that lipid values during the 4-5-week period after study drug administration may reflect the impact of evolovumab if the participant is randomized to that agent. The letter is attached in the supplemental study documents.

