- b. Obtaining remnant samples from blood draws in the ED:
 - i. After a patient agrees to participate and signs the ICF, we will access the JHH remnant sample repository to obtain remnant blood from the earliest timepoint at hospital presentation. We will work with the JHBMC Pathology Department to locate and retrieve the samples for analysis of the proposed biomarkers.

5. Inclusion/Exclusion Criteria

- **5.1 Inclusion Criteria** (for the intervention study group)
 - a. Age 25 to 90 years.
 - b. Non-ST-elevation and ST elevation myocardial infarction, with compatible symptoms and ECG changes.
 - c. Permission of attending physician.
 - d. Ability to understand the risk, benefits, and alternatives of participation.
 - e. Ability to administer study drug within one week of hospital presentation.

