- 2) Change in vascular inflammation from the FDG-PET scan obtained during the early post-infarct period and the 25-30 day FDG-PET scan in the evolocumab and placebo groups. Vascular inflammation will be assessed in the average of the TBR (target to background) of the MDS (of most diseased segments) of the carotid artery or aorta in the evolocumab vs. placebo groups. The target to blood pool ratio or TBR is the ratio of the mean activity in the vessel to the venous blood pool. [43]
- 3) Change in myocardial inflammation from the FDG-PET scan obtained during the index hospitalization and the thirty-day FDG-PET scan in the evolocumab and placebo groups.
- 4) Difference in the FDG-PET assessment of vascular inflammation in the MDS of carotid artery or aorta in the evolocumab versus placebo groups at 30 days.
- 5) Difference in the FDG-PET assessment of myocardial inflammation at 25-30 days in the evolocumab and placebo groups.
- 5) Serum markers of inflammation and of endothelial and platelet function in the two randomized groups at 25-30 days.
- 6) Change in serum markers of inflammation and of endothelial and platelet function in the two randomized groups from the index hospitalization to 25-30 days.

Secondary (for the observation study group)

1. Change in levels of inflammatory markers and mediators between the initial hospitalization, during hospitalization and 30-day follow-up

Sample Size Considerations (for the intervention study group)

We are providing power considerations for the primary as well as key secondary endpoints (see Tables 1-3).

Primary endpoints:

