Previously published clinically relevant, drug-induced TBR changes are reported in the range of 5%-15%. [44] The power calculations for a 10% and 15% TBR difference based on a sample size of 50 patients per study arm are outlined in Table 3 below. Table 1 uses a 1-sided p-value of 0.05, under the hypothesis that evolocumab will lower inflammation and will not raise it,

consistent with the approach used in the Dal-PLAQUE study. Calculations are performed using non-parametric statistics accounting for the possibility of non-normally distributed TBR data.

Tables 3: Power calculations using a 1-sided p-value, i.e. only assumes that PCSK9 inhibition will lower TBR in the most diseased segment (MDS) and will not raise TBR.

Table 3			Estimated	Detectable
	N in each group	Median (IQR)	Power at	Point
		TBR in STEMI	10% & 15%	Estimate at
		Population at 30	TBR	70% &
		days	Difference	80% Power
Aorta	N = 50	3.2(2.7-4.0)	88%	-8.1%
MDS			99%	-9.1%
Carotid	N = 50	2.5 (2.1 – 3.0)	97%	-6.4%
MDS			99%	-7.2%

The table above shows good to excellent power to demonstrate a difference of 10%, and an excellent power to show a difference of 15% in the primary outcome.

Mean and standard deviations of anticipated TBR in STEMI population at 30-days:

 \triangleright Aorta MDS: 3.3 ± 0.6

 \triangleright Carotid artery MDS: 2.6 ± 0.4

Since the timepoint of study drug administration may vary between participants hospitalized at JHH and Bayview, we will create a co-variable to document the time period between hospitalization and study drug administration and adjust our analysis accordingly.

Sample Size Considerations (for the observation study group)

Analysis of Lp(a) in 37 patients in the placebo group of the intervention study indicates an increase in Lp(a) (median, IQR) from 64 [41,187] to 82 [37,265] nmol/L from that obtained during the hospitalization and at 30 days. We would like to obtain an earlier value and correlate the findings with other inflammatory markers and mediators. Given the findings in the above analysis, we believe results in 100 additional patients would provide an adequate sample size.

a. Early stopping rules.

The DSMB will perform any interim analysis they require to monitor patient safety and provide reports advising continuation of the study.

10. Study Statistics (observation study):

Statistical Approach

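### For the PET change endpoints, day of first scan is a better timing covariate than the planned hospitalization-to-dose interval, which may capture little or only part of the scan-day variation

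*Protocol*

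**What the plan says.** **Timing covariate.** Protocol Section 9 (Sample Size Considerations, intervention study) gives the reason "Since the timepoint of study drug administration may vary between participants hospitalized at JHH and Bayview" and then the remedy: "we will create a co-variable to document the time period between hospitalization and study drug administration and adjust our analysis accordingly". No other timing covariate is named. Inclusion criterion 5.1 e limits the dose interval: "Ability to administer study drug within one week of hospital presentation".

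**First scan.** Section 4a says "FDG/PET scans are not performed at Hopkins Bayview". Bayview patients transferred to the main hospital may be scanned there. For Bayview patients discharged home, and for "Hopkins patients who could not undergo the scan during their admission because of scheduling issues", Section 4a says that "the first scan will be performed on an outpatient basis". It gives no latest day.

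**Endpoints that use the first scan.** Section 9 secondary item 2 is "Change in vascular inflammation from the FDG-PET scan obtained during the early post-infarct period and the 25-30 day FDG-PET scan". Item 3 is the corresponding myocardial change, but with the first scan placed in the index hospitalization. The SAP key secondary endpoint uses the same index-hospitalization baseline.

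**Existing provision for scan timing.** Section 2.2 b i plans separate PET analyses in "those who did and did not undergo the initial PET scan within 48 hours of study drug administration".

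**SAP.** Between-arm PET comparisons are a t-test or a Mann-Whitney test. The SAP has neither a timing covariate nor the 48-hour split.

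**The concern.** The planned covariate measures time to dose. The change endpoints depend on time to first scan. If uptake falls after infarction, a late first scan starts lower and leaves less time to fall before the 25-30 day scan, so differences in scan day enter the residual of the change comparison. Dosing is confined to about a week, but the outpatient first scan has no stated limit, so scan day could vary more than dose day.

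What is at stake is precision on the SAP key secondary outcome, which is planned at only 80% power for a 30% difference. Assignment is blinded and scan day is set by site and scheduling, so there is little reason to expect scan day itself to differ between arms.

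**Working it through.** **1. The plan's power figure.** Inputs from Section 9: n = 50 per arm, mean 35.4, SD 18.1, difference 30%, so 0.30 × 35.4 = 10.62. SE = 18.1 × √(2/50) = 3.62. Two-sided 0.05: 10.62/3.62 − 1.96 = 0.97, power 83.5% (82.8% with the noncentral t). With the Mann-Whitney efficiency of 0.955, power is 81-82%, which agrees with the stated 80%. One-sided 0.05 gives about 90% and does not agree.

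**2. Share of scan-day variance that the dose covariate removes.** Write first-scan day = dose day + lag. The share removed is r², the squared correlation of dose day with scan day. *Assumption:* dose day uniform on 0-7, independent lag uniform on 0-L. Then r² = 49/(49 + L²).

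| Lag from dose to scan (days) | Share removed |
|---|---|
| 0 | 100% |
| 0-2 | 93% |
| 0-7 | 50% |
| 0-14 | 20% |
| 0-21 | 10% |

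*Assumption, two-site mix:* Bayview share 20-40%, Bayview lag 3-14 days, main-hospital lag 0-2 days and dose day 0-2. The dose covariate removes 2-3% if dose timing is alike at both sites, and 61-64% if Bayview dosing spreads over days 0-7. The 48-hour split removes 75-83% in the same scenarios.

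**3. Effect on power.** Add slope² × Var(scan day) to 18.1². The slopes are assumed, and 18.1 is the plan's baseline SD, not an SD of change. With no scan-day variance, power is 83.5%.

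- Slope 1 unit/day, lag 0-14: Var = (49 + 196)/12 = 20.4. Power is 81.2% unadjusted and 81.7% with the dose covariate.
- Slope 2 units/day, lag 0-21: Var = (49 + 441)/12 = 40.8. Power is 66.9% unadjusted and 68.3% with the dose covariate.

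**4. Simulated SE of the arm difference in myocardial change, relative to no covariate.** Inputs: 50 per arm and CV 18.1/35.4 = 0.51. *Assumptions:* late first scan in 20-40% of patients, second scan on days 25-30, uptake declining exponentially with a half-life of 7, 14 or 28 days.

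| Assumed link between dose day and scan day | Dose-day covariate | First-scan-day covariate |
|---|---|---|
| Unrelated | 1.00-1.01 | 0.83-0.97 |
| Scan follows dose, dosing alike at both sites | 1.00 | 0.84-0.97 |
| Scan follows dose, late-scan patients dosed over days 0-7 | 0.89-0.98 | 0.79-0.95 |

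The 48-hour indicator, used as a two-level covariate, gave 0.83-0.99.

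**5. If uptake does not fall toward zero.** With dose day and scan day unrelated, a plateau at 50% of the initial level cuts the gain to about 0.5-9%. With a plateau at 80% the gain is 2% or less in every scenario tried. Over 54 scenarios that included plateaus, the SE with first-scan day ran from about 20% lower to 0.5% higher than with no covariate. It was never more than 0.1% worse than with dose day.

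**6. Vascular TBR.** The decay model does not carry over. The protocol expects an aortic TBR of 3.3 at 30 days. Decay back from day 27 to day 4 would imply 3.3 × 2^(23/7) = 32, 3.3 × 2^(23/14) = 10 or 3.3 × 2^(23/28) = 6. No gain for TBR is claimed from this model.

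**The case against.** The strongest objection is that dose day and scan day are probably related. The protocol itself says that dose timing may vary between the two hospitals, and site is also one of the reasons for a late first scan. A reader might infer that the planned covariate removes none of the scan-day variation. That would require the two days to be uncorrelated, which the documents do not say. With correlated site timing the dose covariate recovered up to about two thirds of the available gain, and if every scan closely followed dosing it would recover nearly all of it. This objection stands, and the point is limited accordingly.

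Second, the investigators did see the scan-timing problem: Section 2.2 b i plans the 48-hour analyses. That also stands, in part. The split divides 100 patients into subgroups, measures from dose and not from infarction or presentation, and does not appear in the SAP.

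Third, the size of the gain rests on scan days, a late-scan share and a rate of decline that the documents do not give. This stands. The larger gains need a short half-life and many late scans.

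Fourth, scan day is fixed after randomization, and a first scan done after dosing may already carry drug effect. Adjusting for scan day does not remove that effect. This stands as a limit of the remedy. Showing the unadjusted result and the 48-hour split beside the adjusted one makes it visible.

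**Conclusion.** The point holds as a cheap improvement. The plan adjusts for time to dose, while the change-from-first-scan PET endpoints also depend on an interval that has no stated limit and no covariate. For those endpoints first-scan day was as good as or better than dose day in essentially every scenario tried.

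For myocardial uptake the gain runs from essentially none (a high plateau) to about 20% of the SE (7-day half-life, 40% late scans). At that upper end, 1/0.80² = 1.56, so the gain would match the precision of 56% more patients, but only under those assumptions.

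Three wider readings are not supported. The documents do not show that the dose covariate is useless. No gain has been shown for vascular TBR. The 25-30 day PET comparisons do not use the first scan and are unaffected by its timing.

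Separately, the texts disagree: Section 4a allows an outpatient first scan, while Section 9 item 3 and the SAP place it in the index hospitalization. Read literally, patients first scanned as outpatients have no valid baseline for the myocardial change endpoint.

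**What to change.** 1. In protocol Section 9 and the SAP, for the PET change-from-first-scan endpoints only, specify a between-arm regression model with days from hospital presentation to first scan and days to second scan as covariates, instead of or beside hospitalization-to-dose. Dose timing may stay for the blood endpoints.
2. Report the unadjusted comparison beside it, and carry the 48-hour split from Section 2.2 b i into the SAP.
3. Reconcile Section 4a with Section 9 item 3 and the SAP, so that it is clear whether an outpatient first scan counts as the baseline.

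Cost: a few sentences, dates that imaging produces anyway, and one or two degrees of freedom. The covariate is post-randomization, and the adjustment does not correct for any drug effect already present in a first scan done after dosing.

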The primary study outcome will assess the temporal trend in levels of Lp(a) in patients with type I acute myocardial infarction. We will compare the change (absolute and percent) in Lp(a) from the acute myocardial infarction event to subsequent measures using paired t-tests within each population group (non-African and African ancestry). We will also compare the between individual time points, using paired t-tests within each population group. Mixed effects and generalized estimating equation (GEE) models will be used to compare the time courses for Lp(a) change using all available time points within each population group. For all analyses, p-values <0.05 will be used to indicate statistical significance.

Sample Size Considerations

We are providing power calculations for the primary endpoint:

Power calculations for this study are based on the primary outcome of change in Lp(a) levels between the acute myocardial infarction setting and that obtained during a subsequent, stable setting. We anticipate non-acute myocardial infarction median (interquartile range) Lp(a) levels of 17 (7-47) mg/dL (33 nmol/L (12-98) as is true in the general adult US population.[45] The standard deviations for the acute phase (Day 0 and Day 30) as well as for the 30-day follow-up are derived from the ongoing EVACS study.[46] As shown in **Table 4** the total sample size of 100 participants), using a two-sided p-value of 0.05, will have 80% power to detect a minimum difference of 42 nmol/L in Lp(a) at Day 30 (12.5% difference from baseline; **Table 5**). Based on the differences from general adult US population median of 33 nmol/L to the expected 30 day level post infarction of approximately 45 nmol/L based on what we observed in our EVACS study, we will have appropriate power to detect clinically important differences in Lp(a) levels with our sample size of 100.

Table 4:

TUDIC T.		
N=100	Minimum detectable difference [Lp(a), nmol/L]	
Day 0 (SD=101)		
80% Power	29	
85% Power	31	
90% Power	33	
Hospital Day 1-7 (SD=121)	
80% Power	34	
85% Power	37	
90% Power	40	
Day 30 (SD=147)		
80% Power	42	
85% Power	45	
90% Power	50	

Table 5:

N=100	Minimum detectable %- difference from baseline
Hospital Day 1-7 (SD 29)	
80% Power	8
85% Power	9
90% Power	9.5
Day 30 (SD=44)	
80% Power	12.5
85% Power	13.5

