In terms of the African American cohort we anticipate that the Lp(a) changes will be larger [47] and based on our experience in the EVACS study, we anticipate approximately 25% of the enrolled subjects will be African American.[46] Furthermore, we anticipate the non-acute myocardial infarction median (interquartile range) Lp(a) levels of 77 (20-200) nmol/L as published from the Dallas Heart Study [47]. As shown in **Table 5** the sample size of approximately 25 African American participants, using a two-sided p-value of 0.05, will have 80% power to detect a minimum difference of 85 nmol/L in Lp(a) at Day 30 (26% difference from baseline; **Table 6**). Based on the differences from the general US adult African American median of 77 nmol/L to expected 30 day level post infarction of approximately 152 nmol/L based on what we observed in our EVACS study, we will have appropriate power to detect clinically important differences in Lp(a) levels with our sample size of 25.

Table 5:

_ 1 010 10 01	
N=25	Minimum detectable difference [Lp(a), nmol/L]
Baseline (SD=101)	
80% Power	60
85% Power	65
90% Power	70
Hospital Day 1-7 (SD=121)	
80% Power	70
85% Power	75
90% Power	85
Day 30 (SD=147)	
80% Power	85
85% Power	90
90% Power	100

Table 6:

N=25	Minimum detectable %- difference from baseline
Hospital Day 1-7 (SD 29)	
80% Power	17
85% Power	18
90% Power	20
Day 30 (SD=44)	
80% Power	26
85% Power	28
90% Power	30

11. Risks

a. Medical risks, listing all procedures, their major and minor risks and expected frequency.

Study drug:

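### Observation study: the N=100 power for Lp(a) belongs to a pooled paired test that is not written, and no power is given for the larger ancestry group (about 75) that would be tested

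*Protocol*

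**What the plan says.** Protocol Section 10, Statistical Approach, names three Lp(a) analyses for the observation study:

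- Change from the acute event to later measures, "using paired t-tests within each population group (non-African and African ancestry").
- Comparisons of time points: "We will also compare the between individual time points, using paired t-tests within each population group".
- Mixed-effects and GEE models, to "compare the time courses for Lp(a) change using all available time points within each population group".

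No test on all patients together is written. Under Sample Size Considerations, the main power statement nevertheless covers all patients: "total sample size of 100 participants), using a two-sided p-value of 0.05, will have 80% power to detect a minimum difference of 42 nmol/L" at Day 30, given also as a "12.5% difference from baseline". Table 4 and the first of the two tables numbered 5 carry these N=100 figures.

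The section then turns to African American participants, expected to be about 25% of enrolment. It states 80% power for 85 nmol/L (26%) at Day 30 with about 25 patients, supported by two N=25 tables. That part opens: "In terms of the African American cohort we anticipate that the Lp(a) changes will be larger". No power figure appears for the other patients. The SAP covers only the intervention trial.

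**The concern.** A power statement describes a particular test. Here the tests as written have about 75 and about 25 patients, while the leading statement describes a test with 100. A reader would take 80% power for 42 nmol/L as a property of the planned primary analysis, when the larger of the two written tests has less. The group of about 75, three quarters of the cohort, is the one planned analysis with no power figure. Lp(a) trajectory is the primary outcome of the observation study in Sections 9 and 10, so it should be clear which test answers that question and what it can detect. Splitting also gives up precision for the overall trajectory.

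**Working it through.** **Inputs, all from Protocol Section 10.** Two-sided alpha 0.05. Day 30 SD 147 nmol/L (Table 4) and 44 percentage points (first Table 5). Pooled N = 100. African American share about 25%, so n is about 25 and, by subtraction, about 75 for the rest; the 75 is not printed. The SDs are used as given, as SDs of the quantity in a paired (one-sample) test.

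**Formula.** Power = P(T > t(0.975, n−1)), where T is noncentral t with n−1 degrees of freedom and noncentrality d·√n/SD. The detectable change is the d that gives power 0.80. Normal approximation: d = SD × (1.960 + 0.842)/√n.

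**Step 1: reproduce the plan's figures.**
- N = 100, SD 147: approximation 147 × 2.802/10 = 41.2; exact 41.6 nmol/L (stated 42). Power for 42 is 80.8%.
- N = 100, SD 44: exact 12.45% (stated 12.5%). Power for 12.5% is 80.3%.
- n = 25, SD 147: exact 85.9 nmol/L (stated 85). Power for 85 is 79%.
- n = 25, SD 44: exact 25.7% (stated 26%). Power for 26% is 81%.

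Other constructions do not match 42 nmol/L: a one-sided test gives 36.8, and a two-sample comparison of 50 with 50 gives 82.4. The N=100 figures are therefore those of a single pooled paired test.

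**Step 2: the same calculation for the group with no figure (n = 75).**
- Power for 42 nmol/L: noncentrality 42 × √75/147 = 2.47; power 68.5%.
- Power for 12.5%: noncentrality 12.5 × √75/44 = 2.46; power 68.0%.
- 80% detectable change: approximation 147 × 2.802/√75 = 47.6, exact 48.2 nmol/L; on the percent scale 14.2 and 14.4%.

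The ratio of detectable changes is about √(100/75) = 1.15 (1.16 exact), whatever common SD is used.

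| Test | n | Power for 42 nmol/L | Power for 12.5% | 80% detectable change | Power stated in protocol? |
|---|---|---|---|---|---|
| Pooled (not written) | 100 | 80.8% | 80.3% | 41.6 nmol/L; 12.45% | Yes |
| Non-African ancestry | about 75 | 68.5% | 68.0% | 48.2 nmol/L; 14.4% | No |
| African ancestry | about 25 | 27.8% | 27.6% | 85.9 nmol/L; 25.7% | Yes |

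**Step 3: how two separate tests behave if the true change is the same in both groups.** With SD 44 and independent groups, the chance that exactly one is significant is p75(1 − p25) + p25(1 − p75). At a 15% change: 0.830 × 0.627 + 0.373 × 0.170 = 0.58. At other changes: 39% at 8%, 58% at 12.5%, 42% at 20%, 22% at 25% and 10% at 30%. The 12.5% to 15% region is close to the peak.

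**The case against.** Four points can be made for the plan.

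*A pooled test was probably intended.* Sections 9 and 10 both describe the primary outcome as the Lp(a) course in patients with acute myocardial infarction, without a split, and the N=100 power is tied to that outcome. This is plausible, and the defect may be one omitted sentence. But the paired tests that are written are split, so the sentence has to be supplied.

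*The mixed/GEE sentence is ambiguous.* Its closing phrase could attach to the time points, and comparing time courses could mean comparing the two groups' courses in one model. This stands. It is why the point rests on the paired t-tests and asks only for clarification of the models.

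*The African American group is already powered.* Correct, and the figures reproduce. A reader might infer that the stated 80% power is delivered by no planned analysis; that goes too far. The gap is the N=100 claim and the group of about 75.

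*No ancestry comparison was promised.* Also correct. A reader might take the absence of a test for the expected larger change in African American patients as an error. But no objective or outcome asks for that comparison, the expectation introduces the n=25 calculation, and nothing says the two p-values will be set against each other. Nor are conflicting results from the two groups to be generally expected under equal changes: the chance runs from about 10% to 58% over changes of 8% to 30%, and the protocol anticipates unequal changes.

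**Conclusion.** The mismatch is real and moderate. The N=100 power is correct arithmetic for a pooled paired test that the plan does not write. For the written test in the larger group, power at the stated 42 nmol/L or 12.5% is about 68% and not 80%, and the 80% detectable change rises to about 48 nmol/L or 14.4%. The n=25 power statement is sound on its own terms. The missing ancestry contrast is an optional addition.

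This rests on the 25% share holding, on the protocol's SDs applying to both groups, and on no allowance for dropout, since none is given for this study. The SDs are labelled by time point, and whether they describe within-patient change is a separate question. It would move all the absolute figures but not the relative loss from 100 to 75. The intervention trial is unaffected.

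**What to change.** Choose one of two routes in Section 10.

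1. **Pooled primary test.** State the presentation-to-Day-30 change in all patients as the primary contrast, for example from one mixed model with time, ancestry and time × ancestry, and report group-specific changes with 95% CIs from that model. Weight the pooled contrast by the enrolled ancestry mix. An equal-weight average of the two groups has variance SD² × ¼ × (1/75 + 1/25) = SD²/75, which would bring back the precision of 75 patients.
2. **Split kept.** Remove the N=100 claim and give power for about 75 (80% for about 48 nmol/L or 14.4% at the present SDs) beside the existing n=25 figures.

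Under either route, reword the mixed/GEE sentence to say whether the model is fitted to all patients or by group. The time × ancestry estimate with its CI may be added if the investigators want to address the expected difference.

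The cost is wording only: no new patients, samples or visits. Under the second route the stated sensitivity in the larger group becomes less favourable.

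### On the nmol/L scale, the observation study supports its claim of adequate power with a 12 nmol/L Lp(a) difference, against its own stated minimum of 42

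*Protocol*

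**What the plan says.** Protocol section 10, Study Statistics (observation study), sets the analysis under Statistical Approach: "We will compare the change (absolute and percent) in Lp(a) from the acute myocardial infarction event to subsequent measures". The comparison is to be made separately by ancestry, "using paired t-tests within each population group (non-African and African ancestry". Mixed-effects and GEE models over all time points are planned as well.

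Sample Size Considerations in the same section ties its SDs to time points: "The standard deviations for the acute phase (Day 0 and Day 30) as well as for the 30-day follow-up" are attributed to the EVACS study. Table 4 (N=100) lists SDs of 101 at Day 0, 121 at Hospital Day 1-7 and 147 at Day 30. The text says the study "will have 80% power to detect a minimum difference of 42 nmol/L in Lp(a) at Day 30", and equates this with 12.5% on the percent scale. The justification follows: from the "general adult US population median of 33 nmol/L to the expected 30 day level post infarction of approximately 45 nmol/L", the protocol concludes that "we will have appropriate power to detect clinically important differences in Lp(a) levels with our sample size of 100".

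For African American participants ("we anticipate approximately 25% of the enrolled subjects will be African American", so about 25), the pattern repeats. The stated minimum is 85 nmol/L, and the difference offered is from a population median of 77 to an expected 30-day level of about 152. The nmol/L table for N=25 uses the same three SDs, with the first row labelled Baseline.

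Separate percent-change tables use SDs of 29 (Hospital Day 1-7) and 44 (Day 30). Section 9 reports that in 37 placebo patients of the intervention study the median Lp(a) rose from 64 in hospital to 82 nmol/L at 30 days.

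**The concern.** Four things do not fit together on the absolute scale.

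1. The difference cited as detectable, 45 − 33 = 12 nmol/L, is well under a third of the 42 nmol/L stated as the minimum. For African American participants, 152 − 77 = 75 is below the stated 85.
2. The planned test uses within-patient change, but the SDs in the nmol/L tables look like SDs of levels. A Day 0 or Baseline row cannot hold the SD of a change from Day 0.
3. The tests are run within ancestry groups, so the N=100 minimum belongs to no planned t-test.
4. Both justifying sentences set a general-population median against post-infarct patients. That is a different contrast from the within-patient primary outcome.

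Absolute change is one of the two planned scales. If it is underpowered for the rise of interest and the protocol says otherwise, a null result in nmol/L could be read as evidence that Lp(a) does not rise.

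**Working it through.** **Method.** One-sample t-test (the same calculation as a paired t-test), two-sided 0.05. Power comes from the noncentral t with n − 1 degrees of freedom and noncentrality δ√n / SD. The normal approximation to the 80% minimum is (1.960 + 0.842) × SD / √n.

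**Step 1: reproduce the tables.** For SD 147 and N=100 the approximation gives 2.802 × 14.7 = 41.2; the exact value is 41.6 (stated 42).

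| Scale, SD | N=100 computed (stated) | N=25 computed (stated) |
|---|---|---|
| nmol/L, 101 | 28.6 (29) | 59.0 (60) |
| nmol/L, 121 | 34.2 (34) | 70.7 (70) |
| nmol/L, 147 | 41.6 (42) | 85.9 (85) |
| percent, 29 | 8.2 (8) | 16.9 (17) |
| percent, 44 | 12.4 (12.5) | 25.7 (26) |

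A one-sided test (36.6) or a two-sample test with 100 per group (58.2) does not reproduce the 42. So each time point's SD was entered as the SD of the difference.

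**Step 2: power for the cited differences, same method, SD 147.**
- 12 nmol/L: 12.8% at N=100 and 10.7% at n=75. About 1,180 patients would be needed for 80%.
- 75 nmol/L at n=25: 68.7%.

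**Step 3: the group sizes actually tested.** With 25% African American participants, the groups are about 75 and 25. At n=75 the minimum is 48.2 nmol/L (SD 147), not 42, and 14.4% (SD 44), not 12.5%.

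**Step 4: the planned paired test, Day 0 to Day 30.** The within-patient correlation r is not given, so it is varied as an assumption. SD of change = √(101² + 147² − 2r × 101 × 147) = √(31,810 − 29,694r).

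| r | SD of change | 80% minimum, N=100 | Power for 12, N=100 | Power for 12, n=75 |
|---|---|---|---|---|
| 0.5 | 130.2 | 36.8 | 15% | 12% |
| 0.9 | 71.3 | 20.2 | 39% | 30% |
| 1 | 46.0 | 13.0 | 73% | 61% |

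For 80% power at 12 nmol/L, the SD of change must be at most 42.4 (N=100) or 36.6 (n=75). Both lie below 46.0, the smallest value these two SDs allow.

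**Step 5: from the in-hospital sample.** SD of change = √(121² + 147² − 2r × 121 × 147) = √(36,250 − 35,574r). Solving for 42.4 gives r = 0.97 (N=100); solving for 36.6 gives r = 0.98 (n=75).

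**Step 6: African American participants, Day 0 to Day 30.** For 75 nmol/L at n=25, 80% power needs an SD of change of 128.4, so r = (31,810 − 128.4²) / 29,694 = 0.52.

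**Step 7: percent scale.** Taking the rise from 64 to 82 as 18/64 = 28% (a ratio of medians, assumed to stand for the mean percent change) with SD 44, power is over 99.9% at n=75 and about 87% at n=25.

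**The case against.** The strongest reply is that the sentence claiming appropriate power names no scale. Read as percentages, 33 to 45 is 12/33 = 36% against a minimum of 12.5%, and 77 to 152 is 75/77 = 97% against 26%; both clear. That stands, and it confines the point to the absolute scale. It does not rescue the text, because the differences are given in nmol/L straight after an nmol/L minimum and the absolute change is also to be tested.

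Second, 12 nmol/L may simply be the wrong input. Lp(a) is skewed, and a gap between medians of two populations is not a mean change. Rough means from the section 9 quartiles, (41 + 64 + 187)/3 = 97 and (37 + 82 + 265)/3 = 128, suggest a rise of about 31 nmol/L. With SDs 121 and 147 and n=75, paired power for 31 is about 50% at r=0.5, 85% at r=0.8 and 98% at r=0.9. Section 9's 30-day median of 82 also sits uneasily beside the 45 attributed to EVACS, though the two may not describe the same patients. This is fair: the low power figures are not estimates of the study's true power. It is also a further reason to replace the justification offered.

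Third, SDs of levels would suit a one-sample comparison of each time point with a fixed population value. That reading is possible, but it is not the stated primary outcome.

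Fourth, mixed-effects and GEE models are also planned and are not evaluated here. True, but the protocol's own minima reproduce as t-tests, and nothing in the power text appeals to those models.

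Finally, the 75-versus-85 gap is mild and disappears in a paired test once r exceeds about 0.52. Accepted.

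**Conclusion.** The concern holds on the absolute scale. The protocol justifies N=100 with a 12 nmol/L difference that has about 13% power by its own method. For Day 0 to Day 30, the planned paired test cannot reach 80% for that difference at any correlation, given the protocol's SDs; from the in-hospital sample it needs r of about 0.97 to 0.98.

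That the tabulated SDs describe levels is an inference, but a strong one, resting on the Day 0 and Baseline rows and the attribution to time points. The paired figures assume that reading, treat the SDs as exact, and take differences of medians as mean changes. They show that the text is inconsistent; they do not show that 100 patients are too few. With high correlation the true minimum would be below 42.

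The percent-scale figures reproduce and may well be adequate. The randomised comparison is untouched. The text should be corrected, since it is the power justification for the observation study's primary outcome.

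**What to change.** - Recompute the absolute-scale minimum detectable change for the planned paired test from the SD of within-patient change, preferably on log Lp(a) because of the skew. Use the 37 placebo patients already analysed, and state which pair of time points they supply: section 9 describes in-hospital and 30-day values, while section 10 implies that EVACS also has Day 0 data.
- Report the result at n of about 75 and 25, with the precision of the SD. If 25% of the 37 (about 9) are African American, the 95% confidence interval for that group's SD runs from √(8/17.53) = 0.68 to √(8/2.18) = 1.92 times the estimate, assuming normality.
- Reword both statements of appropriate power to name the scale, and base them on an expected within-patient change instead of a population median.
- Label 12.5% and 26% as separate percent-change calculations, and restate the N=100 percent minimum at n of about 75 (14.4%).

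The cost is a rewrite of the sample-size text and the two nmol/L tables from existing data, with no added patients, visits or samples. Stated power would probably become more modest on the absolute scale and may stand on the percent scale.
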